#### **12.6.5.4 Clinical Laboratory Evaluation**

Table 20 lists the hematology, clinical chemistry and urine analysis parameters to be assessed in this study.

#### **Table 20 List of Laboratory Safety Parameters**

Hematology	Clinical Chemistry	Urine Analysis

• Hematocrit

• Hemoglobin

• Mean corpuscular

	

• Albumin

• Total protein

• Alkaline phosphatase

	

• pH

• Bilirubin

• Glucose

#### **Confidentiality Statement**

Data and information contained in this document are considered to constitute trade secrets and confidential commercial information, and the legal protections provided to such trade secrets and confidential information are hereby claimed under the provisions of applicable law. No part of this document may be publicly disclosed without the written consent of Philip Morris Products S.A.

---

hemoglobin	• Alanine aminotransferase	• Nitrite
• Mean corpuscular hemoglobin concentration	• Aspartate aminotransferase	• Red blood cell traces
• Mean corpuscular volume	• Blood urea nitrogen	• Protein
• Platelet count	• Creatinine	• Specific gravity
• Red blood cell count	• Gamma-glutamyl transferase	
• White blood cell (WBC) count	• Fasting glucose*	
• Differential WBC count:	• Lactate dehydrogenase	
✓ Neutrophils	• Potassium	
✓ Basophils	• Sodium	
✓ Eosinophils	• Total bilirubin	
✓ Lymphocytes	• Direct bilirubin	
✓ Monocytes	• Total cholesterol	
	• Triglycerides	

---

\* Except at Screening where non-fasting glucose will be assessed

Any clinical safety laboratory test result will be reviewed by the Investigator and assessed for clinical significance.

Subjects with clinically significant abnormal laboratory values at Screening have not to be enrolled. Abnormal laboratory test results detected at the Screening Visit whose CTCAE grades are 2 or higher or still are CTCAE grade 1 and deemed clinically significant are usually concomitant disease or a manifestation of one and must be recorded accordingly. However, in some instances, they may be assessed as AEs or as manifestations of already reported AEs. This decision will require a careful assessment of the abnormal result within the clinical context on a case-by-case basis and will depend on the Investigator's medical judgment.

Abnormal laboratory test results detected after the Screening Visit whose CTCAE grades are 2 or higher or still are CTCAE grade 1 and deemed clinically significant must be either recorded as AEs or linked to a concomitant disease or still to an already reported AE.

The grading scheme used in the Common Terminology Criteria for Adverse Events and Common Toxicity Criteria [CTCAE] version 4.03) will be used by the Investigator to assess abnormal laboratory AEs. These CTCAE grades will be derived programmatically and are available in the SDTM laboratory dataset.

Laboratory actual values and changes from baseline will be listed and summarized at Screening, Baseline, and post product use by product variant for assessments performed at Day 2-5 or at time of discharge referring to product used at Day 1-4 (i.e. assessments performed on Day 2 are related to P3P 3 used on Day 1) (Listings 15.3.6.3, 15.3.6.4 and 15.3.6.5). The number and percentage of subjects with normal/abnormal not clinically significant/abnormal clinically significant results will be tabulated for laboratory parameters (Tables 15.2.6.10.1, 15.2.6.11.1 and 15.2.6.12.1).

Listings for the clinical laboratory data will include the following information: normal/high/low (with respect to the reference range) or normal/abnormal (with respect to the reference value), clinically significance (as defined by the Investigator), the change

---

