7.6 Laboratory Assessments

7.6.1 Clinical Chemistry, Hematology, and Urine Analysis Safety Panel

A blood sample for hematology and clinical chemistry analysis will be taken from each subject at Screening, Admission and Day 2 to Day 5. Subjects should be fasting for at least 6 hours prior to sampling, except at Screening where non-fasting samples can be used. Tests will be conducted at a local laboratory (Appendix B). A urine sample will also be collected from each subject for urine analysis. Parameters to be tested are listed in Table 4.

Confidentiality Statement

Data and information contained in this document are considered to constitute trade secrets and confidential commercial information, and the legal protections provided to such trade secrets and confidential information are hereby claimed under the provisions of applicable law. No part of this document may be publicly disclosed without the written consent of Philip Morris Products S.A.

Table 4 Clinical Laboratory Parameters for Safety Panel

Hematology	Clinical Chemistry	Urine Analysis

 • Hematocrit • Hemoglobin • Mean corpuscular hemoglobin • Mean corpuscular hemoglobin concentration • Mean corpuscular volume • Platelet count • Red blood cell count • White blood cell (WBC) count • Differential WBC count: 
 • Neutrophils • Basophils • Eosinophils • Lymphocytes • Monocytes 	
 • Albumin • Total protein • Alkaline phosphatase • Alanine aminotransferase • Aspartate aminotransferase • Blood urea nitrogen • Creatinine • Gamma-glutamyl transferase • Fasting glucose* • Lactate dehydrogenase • Potassium • Sodium • Total bilirubin • Direct bilirubin • Total cholesterol • Triglycerides 	
 • pH • Bilirubin • Glucose • Nitrite • Red blood cell traces • Protein • Specific gravity

* Except at Screening where non-fasting glucose will be assessed

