9.3 Investigational Period (Day 1 to Day 4)

At each assessment day subjects will use the assigned product for the given visit with two product use regimen:

- fixed puffing regimen comprising of 12 puffs in total at a rate of one inhalation every 30 seconds (\pm 5 seconds) in the morning.
- ad libitum* use period for 60 minutes (\pm 5 minutes) in the afternoon.

The study activities performed in the morning (prior to and related to fixed puffing) for Days 1, 2, 3 and 4 are listed in Table 9. The study activities performed in the afternoon (related to *ad libitum* product use and post product use activities) are listed in Table 10. The start of each product use regimen will be separated by at least 10 hours.

Table 9 Time Schedule – Fixed puffing period (Day 1, 2, 3, 4 - Morning)

Time	Blood Sample	Procedures	Additional Information
Start of Procedure			
Prior to product use	✓	Blood sampling for CYP2A6 assessment	Day 1 only
Prior to product use	✓	Clinical laboratory parameters (hematology, clinical chemistry)	After at least 6 hours of fasting. Day 2, 3 and 4
Prior to product use		Urine analysis safety panel	Day 2, 3 and 4
Prior to product use		Cough assessment	Day 2, 3 and 4. 24 ± 1 hour after T_0 fix for the product used on the previous day
Prior to product use at Day 2		Randomization	Day 2 only. Discontinuation of supernumerous subjects, if applicable, should occur prior to randomization
Prior to product use (within 2 hours)		Assembly and weighing of product	
Prior to product use (within 1 hour)		Vital signs (blood pressure, pulse rate, respiratory rate)	At least 5 min in supine position prior to measurement.
15 \pm 5 minutes prior to T_0 fix	✓	Blood sampling for baseline nicotine level for fixed puffing	

Confidentiality Statement

Data and information contained in this document are considered to constitute trade secrets and confidential commercial information, and the legal protections provided to such trade secrets and confidential information are hereby claimed under the provisions of applicable law. No part of this document may be publicly disclosed without the written consent of Philip Morris Products S.A.

Time	Blood Sample	Procedures	Additional Information
Start of Procedure			
15 ± 5 minutes prior to T_0 fix		VAS-craving: baseline for fixed puffing	
Just before product use		Piercing of P3P capsule	

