In general, all safety data will be listed and tabulated using the approach described in section 12.1.3. Safety variables collected during exposure periods will also be reported by product exposure.

AE data will serve for the primary assessment of safety. Other safety variables monitored in this study include: incidence and frequency of P3P product events including malfunction/misuse; respiratory symptoms (cough assessment VAS and Likert scales); vital signs (systolic and diastolic blood pressure, pulse rate, respiratory rate); spirometry; ECG data; clinical chemistry, hematology, and urine analysis safety panel; physical examination; concomitant medications.

All safety data will be listed and AEs will be summarized by product variant (fixed puffing regimen and *ad libitum* use periods will be combined at the product variant level). Safety measurements assessed both after fixed puffing regimen and *ad libitum* use (vital signs, ECG etc.) will be summarized per fixed puffing/*ad libitum* use regimen and product variant.

Confidentiality Statement

Data and information contained in this document are considered to constitute trade secrets and confidential commercial information, and the legal protections provided to such trade secrets and confidential information are hereby claimed under the provisions of applicable law. No part of this document may be publicly disclosed without the written consent of Philip Morris Products S.A.

The number and percentage of subjects with AEs, SAEs, and product events will be tabulated by system organ class and preferred term. Summaries will also be presented for AEs leading to discontinuation, AEs leading to death, AEs by relatedness to product exposure (with and without laboratory related AEs), AEs by severity, and laboratory AEs. Tabulations will be performed for both the number of subjects experiencing an event and the number of events.

Safety laboratory assessments are performed on Day 2 to Day 5 in the morning prior to product use (Appendix A). Any lab related AEs will be assigned to the product used on the previous day.

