## 4.1 Definitions for Statistical Analysis

The following special terms are used in this SAP:

Baseline	For PK/PD analysis and VAS-craving assessment, baseline is defined as the last assessment prior to time point of start of product use at the fixed puffing regimen ( $T_0 \text{ fix}$ ) for fixed puffing regimen and as the last assessment prior to time point of start of first product use at the ad libitum use period ( $T_0 \text{ ad lib}$ ) for ad libitum use, for each study day of exposure. For all the other endpoints, the baseline is defined as the last available assessment prior to $T_0 \text{ fix}$ on Day 1, except for vital signs, where baseline is defined as the last assessment prior to $T_0 \text{ fix}$ for each study day of exposure.
Safety follow-up	After discharge on Day 5 or after discontinuation, a 7-day safety follow-up will be done
End of Study	The end of the study (EOS) for a subject is defined as either the Discharge at Day 5, or the date of early termination of the subject, plus the 7 days for the Safety Follow-up Period. The end of the whole study corresponds to the individual EOS of the last subject.
Enrollment	On Admission Visit for eligible subjects after all applicable inclusion and exclusion criteria have been satisfactorily assessed and met.
Randomization	Assignment to the respective sequence of product use at Day 2.
Screen failure	Subject who signs the ICF but is not enrolled.

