#### **Confidentiality Statement**

0.0001 will be displayed as 0. The geometric coefficient of variation (CV) will be reported as % with two decimal digits.

- For categorical data, frequency counts and percentages will be presented, missing values will be regarded as an own category if any missing value exists. Percentages will be presented to one decimal place. Percentages will not be presented for zero counts.

All analyses and summaries will be performed by product and overall, and separately for fixed and *ad libitum* use regimen when applicable.

Unless otherwise specified, summaries will be presented at Baseline and at each post baseline timepoint, including the change from baseline (calculated as difference from baseline).

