#### Confidentiality Statement

Data and information contained in this document are considered to constitute trade secrets and confidential commercial information, and the legal protections provided to such trade secrets and confidential information are hereby claimed under the provisions of applicable law. No part of this document may be publicly disclosed without the written consent of Philip Morris Products S.A.

---

from baseline and the CTCAE grade. Only CTCAE grades greater than zero will be presented.

Descriptive statistics will be presented for actual values and changes from baseline (Table 15.2.6.10.2, Table 15.2.6.11.2 and Table 15.2.6.12.2), tables of frequency will be presented for qualitative values (Table 15.2.6.12.3) and shift tables from baseline will be provided (Tables 15.2.6.10.3, 15.2.6.11.3, 15.2.6.12.4 and 15.2.6.12.5).

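### A laboratory change or shift that persists is repeated under every later variant, which inflates the P3P 1, 2 and 4 columns relative to P3P 3

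*SAP*

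**What the plan says.** - **Baseline.** SAP 4.1 sets a separate baseline for each day and regimen for PK/PD and VAS craving. The remaining endpoints share one reference point, the start of fixed puffing on Day 1: "For all the other endpoints, the baseline is defined as the last available assessment prior to" that time. Among them only vital signs are exempted and get a new reference every exposure day: "except for vital signs, where baseline is defined as the last assessment prior to" that morning's first use. Laboratory data are not in that exception.
- **Samples.** Protocol 7.6.1: "A blood sample for hematology and clinical chemistry analysis will be taken from each subject at Screening, Admission and Day 2 to Day 5". There is none on Day 1, so the scheduled laboratory baseline is Admission. Screening would stand in if the Admission sample were missing.
- **Attribution.** SAP 12.6.5.4 summarises values and changes "post product use by product variant for assessments performed at Day 2-5 or at time of discharge referring to product used at Day 1-4". It adds that "shift tables from baseline will be provided" and tabulates counts of normal and abnormal results. SAP 12.1.3 states the general rule: "All analyses and summaries will be performed by product and overall".
- **Order.** P3P 3 is on Day 1 for everyone. P3P 1, 2 and 4 follow in six sequences of three subjects (Protocol 6.3 and 12.2).
- **Pre-use samples.** Protocol 12.6.3: "Safety laboratory assessments are performed on Day 2 to Day 5 in the morning prior to product use". Protocol Table 9 marks the pre-use blood sample "After at least 6 hours of fasting. Day 2, 3 and 4".

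No rule limits a shift to new onset or flags a finding already present under an earlier variant.

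**The concern.** Vital signs are re-baselined on each exposure day. Laboratory results are not, yet both are reported by variant. A result that moves away from the Admission value after one variant and stays there is entered as a change or shift under that variant and again under each one that follows. P3P 3 can pass a finding on but cannot receive one. A column-by-column reading could therefore show more laboratory change under the 2 mg variants than under the 1 mg variant when nothing differs between them. It could also hide a lasting effect of P3P 3 by spreading it evenly over all four columns.

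Laboratory change from baseline is a listed safety endpoint (Protocol 3.2). The laboratory tables are marked for safety reporting (SAP Table 21), and no model adjusts them for day or sequence.

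**Working it through.** **1. The plan's own figure.** 3! = 6 sequences × 3 subjects = 18 randomized, as stated. There is no power calculation to reproduce.

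**2. How often one finding is shown.** A finding that lasts to Day 5 appears under 4 variants if it starts on Day 1, 3 if on Day 2, 2 if on Day 3 and 1 if on Day 4. Four onsets give 4 + 3 + 2 + 1 = 10 shifted results.

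**3. One variant is the only cause (risk r).** Each of P3P 1, 2 and 4 falls on each of Days 2, 3 and 4 in 6 subjects, and each precedes each of the others in 3 of 6 sequences.
- P3P 4 the cause, full persistence: P3P 4 shows r, P3P 1 and P3P 2 show r/2 each, P3P 3 shows 0. If all 18 subjects were affected, that is 18, 9, 9 and 0.
- P3P 3 the cause, full persistence: all four columns show r.
- With 50% daily persistence the inherited share is (2×0.5 + 1×0.25)/6 = 0.21r for P3P 4 as cause. For P3P 3 as cause it is (0.5 + 0.25 + 0.125)/3 = 0.29r.

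**4. No difference between variants.** The documents give neither onset risk nor persistence, so both are assumed. Let every subject be normal at Admission, h the daily onset risk for a normal subject, and s the chance that an abnormal result is still abnormal next day. With a(0) = 0, the proportion abnormal after day d is

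a(d) = s·a(d−1) + h·[1 − a(d−1)].

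Over 18 subjects without dropout, the expected number is 18·a(1) for P3P 3 and 18·[a(2)+a(3)+a(4)]/3 for each other variant. For h = 5% and s = 1, a = 0.0500, 0.0975, 0.1426, 0.1855. That gives 0.90 and 2.55 subjects, a ratio of 2.84.

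Ratio of each 2 mg column to P3P 3:

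| h per day | s = 1 | s = 0.8 | s = 0.5 | s = 0 |
|---|---|---|---|---|
| 2% | 2.93 | 2.34 | 1.67 | 0.98 |
| 5% | 2.84 | 2.27 | 1.62 | 0.95 |
| 10% | 2.68 | 2.14 | 1.53 | 0.91 |

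**5. A longer P3P 3 window.** SAP 6.3.1 has subjects confined from the evening of Day -1 but does not time the Admission sample. If that sample is taken in the evening, the P3P 3 window is about 1.5 days. With h = 5% and s = 1, P3P 3 shows 1 − 0.95^1.5 = 0.0741. The other columns show the mean of 1 − 0.95^t at t = 2.5, 3.5 and 4.5, which is 0.1636. The ratio is 2.21 (2.28 at h = 2%).

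**6. Counting new onsets from the pre-use sample instead.** With h = 5%, s = 1 and one-day windows, the expected numbers are 0.90 for P3P 3 and 0.81 for each other variant, a ratio of 0.90. It is below 1 because fewer subjects are still normal. With the 1.5-day window, the risk ratio among subjects still normal is 0.05/0.0741, about 0.67.

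**7. Is a persisting drift plausible?** Protocol 2.3.2 names anemia as a risk of the total blood volume drawn. The volumes in Protocol 7.7.1 reproduce the stated total: 77×5 + 4 + 6×12.5 = 464 mL. From the Admission sample up to the Day 2 sample, 12.5 + 4 + 18×5 = 106.5 mL is drawn. Each further day adds 12.5 + 90 = 102.5 mL, giving 209, 311.5 and 414 mL by Days 3, 4 and 5. A hematology drift with blood loss would thus reflect 106.5 mL under P3P 3 and 311.5 mL on average under each other variant. This shows a possible route, not a rate.

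**The case against.** A single baseline taken before any product use is a defensible choice, and several limits on the point stand.

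- **The tables are not the only source.** A reader might infer that the first variant an abnormality followed cannot be recovered. The documents do not support that. Laboratory AEs are assigned to the previous day's product (Protocol 12.6.3) and by start time (SAP 12.6.5.1). Protocol Table 6 has a persisting finding linked to an AE already reported, or not reported again. The listings carry change, reference-range flag, clinical significance and CTCAE grade, so onset can be traced by subject.
- **The normal/abnormal counts use no baseline.** They repeat persistent findings because each day's result is charged to the previous day's variant. A new baseline alone would not alter them.
- **The by-variant layout of the shift tables is inferred** from SAP 12.1.3 and 12.6.5.4. Their titles in SAP Table 21 do not mention variant.
- **P3P 3 on Day 1 is a design decision** made for safety reasons. Variant and day stay confounded for P3P 3 under any baseline.
- **Replacing the Admission baseline has its own faults.** Each morning sample on Days 2 to 4 would be one variant's result and the next one's baseline, so a single noisy value moves two columns in opposite directions. The no-difference ratio could also fall to about 0.67 (step 6), against P3P 3.
- **The study is descriptive.** It has 18 randomized subjects, no hypothesis and no claims drawn from intervals, so no error rate is affected.

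These points argue against discarding the planned tables. They do not remove the repetition from those tables.

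**Conclusion.** The point holds for the laboratory change tables and, by implication, the shift tables. Among P3P 1, 2 and 4, with no true difference, the carry-forward favours none of them; a true and fully persistent effect of one has its contrast with the other two halved. The systematic distortion is P3P 3 against the rest.

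The ratios of 2.84, 1.62 and 0.95 for full, 50% and no daily persistence rest on an assumed 5% daily onset risk, equal for all variants, and one-day windows. A 1.5-day P3P 3 window lowers the full-persistence figure to 2.21. In absolute terms the worst of these 5% cases is about 0.9 against 2.6 subjects. This is a reporting weakness in descriptive safety tables that is cheap to repair. It gives no ground for saying that the trial's safety conclusions would be wrong.

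**What to change.** Keep the Admission-baseline tables as planned. In SAP 12.6.5.4 add, by variant:

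- (a) the number of subjects with a new or worsened abnormality relative to the last sample before that variant's first use, which is Admission for P3P 3 and the same-morning Day 2, 3 or 4 sample for the variant used that day;
- (b) the change from that pre-use sample.

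State in SAP 12.6.5.4 whether the shift tables are by variant. Footnote the new columns to say that P3P 3 is confounded with Day 1 and the product test, that its window may be longer than the others, and that each morning sample serves as one variant's result and the next variant's baseline.

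The cost is SAP wording, one derived baseline variable and extra table columns; no new samples are needed. Two drawbacks remain. An effect that takes more than about 24 hours to appear is charged to the next variant, as it already is under the previous-day rule. A resolving abnormality will show as an improvement under the variant that follows.

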#### Confidentiality Statement

Data and information contained in this document are considered to constitute trade secrets and confidential commercial information, and the legal protections provided to such trade secrets and confidential information are hereby claimed under the provisions of applicable law. No part of this document may be publicly disclosed without the written consent of Philip Morris Products S.A.

---

from baseline and the CTCAE grade. Only CTCAE grades greater than zero will be presented.

Descriptive statistics will be presented for actual values and changes from baseline (Table 15.2.6.10.2, Table 15.2.6.11.2 and Table 15.2.6.12.2), tables of frequency will be presented for qualitative values (Table 15.2.6.12.3) and shift tables from baseline will be provided (Tables 15.2.6.10.3, 15.2.6.11.3, 15.2.6.12.4 and 15.2.6.12.5).

### **12.6.5.5 Vital Signs, Physical Findings and Other Observations Related to Safety**

#### **12.6.5.5.1 Prior and Concomitant Medication**

Prior medication is defined as any medication that started and ended prior to Screening. Concomitant medication is defined as any medication starting on or after Screening. Medications that started prior to Screening and are ongoing at Screening are considered as concomitant.

All medications will be listed by P3P variant and exposure period using PT and Anatomical Therapeutic and Chemical (ATC) codes (World Health Organization - Drug Dictionary Enhanced [WHO-DDE] September 2017 C format). A flag will be presented on the listing indicating whether the medication is prior or concomitant.

Prior and concomitant medications will be listed (Listing 15.3.6.6). Listing will display original dates (no imputation). Prior and concomitant medications will be summarized for the Safety population showing the number (%) of subjects who used the medication at least once by sequence and by ATC 1st and 2nd levels medical term and by preferred drug name (Tables 15.2.6.13.1, 15.2.6.13.2, 15.2.6.14.1 and 15.2.6.14.2).

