#### Confidentiality Statement

- Per-puff parameters and per-product use experience parameters

4. To estimate the amount of powder aerosolized from P3P from the fixed puffing regimen and the *ad libitum* use periods.

Endpoint:

- Weight difference of P3P before and after use

5. To monitor the safety and tolerability during the study.

Endpoints:

- Incidence of adverse events (AEs), serious adverse events (SAEs)
- Frequency of AEs, SAEs
- Incidence of P3P product events including malfunction/misuse
- Frequency of P3P product events including malfunction/misuse
- Physical examination changes from baseline
- Cough changes from baseline (VAS and three Likert scales)
- Electrocardiogram (ECG) changes from baseline (heart rate, PR, QRS, QT, QTcB, QTcF intervals)
- Vital signs changes from baseline (systolic and diastolic blood pressure, pulse rate and respiratory rate)
- Spirometry changes from baseline (FEV1, FEV1 % predicted, FVC, FVC % predicted FEV1/FVC)
- Changes from baseline in clinical chemistry, hematology, and urine analysis safety panel
- Concomitant medications

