## 12.6.5 Safety Evaluation

Safety variables monitored in this study include: AEs; vital signs (systolic and diastolic blood pressure, pulse rate, respiratory rate); spirometry; ECG data; concomitant medication, clinical chemistry, hematology, urine analysis safety panel, BMI, physical examination, respiratory symptoms (cough assessment).

The primary analysis of Safety parameters will be conducted on the Safety population as described in Section 12.1.3 "Descriptive Statistics".

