### 12.6.5.1 Safety Reporting

Safety data will be tabulated on the safety population by exposure period defined as:

- Pre-dose Period: Prior to any Product Use [ICF , first use of P3P 3 test at Day-1[. According to protocol, first use would be P3P 3 product test at Day-1].
- Product Test Period: [First use of P3P 3 test at Day-1, First use of P3P 3 at Day 1[
- P3P 3 Period: [First use of P3P 3 at Day 1, First use of product at Day 2 or time of discharge[
- P3P 1 Period: [First use of P3P 1, First use of the next product variant or time of discharge[
- P3P 2 Period: [First use of P3P 2, First use of the next product variant or time of discharge[
- P3P 4 Period: [First use of P3P 4, First use of the next product variant or time of discharge[
- Safety Follow-Up Period : [from time of discharge, 7 days after discharge].

Safety data will be assigned to the specific safety period where the collection time or start time of the AE is included between beginning and the end of the period.

All AEs occurring from the time of signing of informed consent will be recorded and listed.

Only product emergent AEs will be summarized (the ones occurring during pre-dose period will be listed only). If an AE occurs during the Safety follow up period, then this AE will not be assigned to the last product used but summarized in the Safety Follow-Up Period.

A product emergent AE is defined as an AE that occurs after first P3P product use or that is present prior to first product use and becomes more severe after first product use. All other AEs will not be summarized but provided in listings only.

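### The concomitant medication tables are set out by sequence instead of by exposure period, so they cannot show which P3P variant was in use

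*SAP*

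**What the plan says.** Concomitant medication is an endpoint under the safety objective: SAP 5.2 lists "Concomitant medications", and SAP 12.6.5 includes it among the safety variables ("ECG data; concomitant medication, clinical chemistry, hematology, urine analysis safety panel").

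Three SAP statements govern how it is shown:

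- **SAP 12.6.5.5.1** summarises prior and concomitant medication in the Safety population. The tables are described as "showing the number (%) of subjects who used the medication at least once by sequence and by ATC 1st and 2nd levels medical term"; a breakdown to the level of preferred drug name is added. For the listing, the same section says "All medications will be listed by P3P variant and exposure period".
- **SAP 12.6.5.1** says "Safety data will be tabulated on the safety population by exposure period defined as" seven periods: pre-dose, product test, one for each of the four variants, and safety follow-up.
- **SAP 12.1.3** says "All analyses and summaries will be performed by product and overall, and separately for fixed and" *ad libitum* use where that applies. Protocol 12.1.3 has the same rule.

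Protocol 12.6.3 adds "Safety variables collected during exposure periods will also be reported by product exposure". A separate paragraph of that section names the other safety variables, ending "urine analysis safety panel; physical examination; concomitant medications".

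**The concern.** In this crossover a sequence is an order of use, not an exposure. Grouping medication by sequence mixes use under all four variants within each column. A reader who wants to know whether medication was needed more often under one variant will not find it in these tables, although the neighbouring AE tables (SAP 12.6.5.2) are by exposure period.

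There is also a population mismatch. The tables are for the Safety population, which SAP 10.5 opens to anyone exposed from the Day -1 product test who has a later safety assessment. A sequence is assigned only on the morning of Day 2. Subjects who use P3P 3 and leave before then, including any held back on safety grounds and any supernumerary subjects, have no sequence.

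At stake is whether the tables for a named endpoint say anything about the variants that the safety objective concerns.

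**Working it through.** **Inputs**

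- Six sequences for Days 2 to 4 (SAP Table 1), each preceded by P3P 3 on Day 1 (SAP 6.1).
- Three subjects per sequence (SAP 8).
- Safety population from first exposure, including the product test (SAP 10.5).

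**Step 1. The plan's own figure.** 6 sequences × 3 subjects = 18 randomized, as SAP 8 states.

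**Step 2. Variants in each sequence**

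| Sequence | Day 1 | Day 2 | Day 3 | Day 4 | Variants used |
|---|---|---|---|---|---|
| 1 | 3 | 2 | 4 | 1 | 1, 2, 3, 4 |
| 2 | 3 | 4 | 1 | 2 | 1, 2, 3, 4 |
| 3 | 3 | 1 | 2 | 4 | 1, 2, 3, 4 |
| 4 | 3 | 1 | 4 | 2 | 1, 2, 3, 4 |
| 5 | 3 | 2 | 1 | 4 | 1, 2, 3, 4 |
| 6 | 3 | 4 | 2 | 1 | 1, 2, 3, 4 |

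**Step 3. Can the table separate variants?** Take the most extreme case: all 18 subjects take a drug, but only during the period of one variant *v*.

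- By sequence, each column reads 3/3, because every sequence contains *v*. Setting *v* to P3P 1, 2, 3 and 4 in turn gives four scenarios and one identical table.
- By exposure period, the column for *v* reads 18/18 and the other three variant columns read 0/18. The four scenarios give four different tables.

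**Step 4. Column size.** One user is 1/3 = 33.3% of a sequence column and 1/18 = 5.6% of a variant column, taking the 18 planned randomized subjects. This shows only that the denominators differ; it is not evidence of bias. The P3P 3 column could exceed 18, because exposed subjects who were not randomized belong in it.

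**Step 5. What an allocation by period needs.** Protocol 7.4.4 records medication start and stop by day, month and year. The periods of SAP 12.6.5.1 change at first product use within a day, or at discharge. A drug dated on a changeover day therefore cannot be placed from its date alone. SAP 12.6.5.1 assigns data by collection time or AE start and gives no rule for a medication that runs across periods.

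**The case against.** **The information is planned for.** Listing 15.3.6.6 is by variant and exposure period, and with 18 randomized subjects it can be read by hand. This stands, and it limits the point to the summary tables. A reader might infer that the plan leaves the endpoint unable to inform tolerability by variant. The documents do not support that: the listing carries the attribution, and AE data, which Protocol 12.6.3 makes the primary safety assessment, are tabulated by exposure period.

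**Non-randomized subjects may still be counted.** A reader might infer that they are left out. SAP 12.1.3 requires an overall presentation, and an overall column on the Safety population would include them. What stands is that no sequence column is defined for them.

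**The protocol conflict is softer than it looks.** The protocol asks for reporting by product exposure; it does not speak of tabulation by exposure period, and a listing by variant arguably satisfies it. Where it spells out summaries by variant, it does not name medication. This stands. The firm conflict is with SAP 12.6.5.1 and the by-product-and-overall rule.

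**It may be loose wording.** The AE counting rule in SAP 12.6.5.2 also counts a subject once per sequence, although those tables are by exposure period. The titles of Tables 15.2.6.14.1 and 15.2.6.14.2 mention no sequence, and layout is left to table shells that are not available here. That is plausible, but as written the text specifies sequence. It gives no reason for an exception, and the changes from the protocol that appear in the SAP do not mention one.

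**Conclusion.** The point holds as an inconsistency within the SAP, confined to Tables 15.2.6.14.1 and 15.2.6.14.2. As specified, their sequence columns carry no information on which variant was in use, and exposed subjects who were never randomized have no sequence column. The variant-level information survives only in Listing 15.3.6.6.

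The size is modest. Medication is a descriptive, supporting safety endpoint, and neither the AE tables by period nor the primary PK analysis is affected. The correction is worth making because it is cheap and lets the tables for a named endpoint describe the variants.

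This rests on two assumptions: that the tables are programmed as SAP 12.6.5.5.1 reads, and that subjects complete their sequence. A subject who stops early has not used all four variants, but a sequence column still would not show which variant was in use. The point does not extend to prior medication, which ended before Screening and belongs to no variant.

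**What to change.** In SAP 12.6.5.5.1:

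1. For concomitant medication (Tables 15.2.6.14.1 and 15.2.6.14.2), replace the grouping by sequence with the exposure periods of SAP 12.6.5.1 plus an overall column. Use as denominator the safety subjects exposed in each period.
2. State that a medication spanning several periods counts once in each. Medication already ongoing at Screening would then appear in every period that it covers.
3. Give a rule for a start or stop known only to the day when that day is a changeover, for example counting the medication in both periods.
4. Present prior medication (Tables 15.2.6.13.1 and 15.2.6.13.2) overall only.

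The cost is a short allocation rule, revised column headings and some reprogramming. No new data are needed if the day-level rule is adopted, and the rule can also serve Listing 15.3.6.6, which already has to place medications by variant and period.
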